## Objectives

AIM #1. The primary objective of the study is to investigate the effect of levodopa on cardiovascular autonomic function in participants with PD (with and without OH) Participants with PD+OH and PD-OH will undergo autonomic testing of baroreflex cardiovagal and sympathetic noradrenergic functions on and off of levodopa on two separate days. The primary endpoint will be the change in systolic blood pressure from supine to tilt at 3 minutes. Results of autonomic testing on levodopa will be compared to testing off levodopa in all participants. Each patient will be his or her own control. Secondary endpoints will include validated indices of baroreflex cardiovagal and baroreflex sympathetic noradrenergic functions. Although levodopa may have a mild hypotensive effect, we hypothesize that levodopa will not induce or worsen the drop in blood pressure from supine to tilt at 3 minutes and will not worsen neurogenic orthostatic hypotension. Planned secondary endpoints will also investigate the differences in orthostatic vital signs with active standing and tilt table testing in patients with PD and the relationship between autonomic testing and the orthostatic symptom severity questionnaire.

**AIM #2.** Determine if levodopa has a different effect on cardiovascular autonomic function in participants with PD+OH compared to participants with PD-OH

The data from autonomic testing performed for AIM#1 will be used to assess AIM#2. The primary endpoint for AIM#2 will be indices of baroreflex cardiovagal and noradrenergic function. We hypothesize that levodopa will not alter baroreflex cardiovagal and sympathetic noradrenergic functions in either PD+OH or PD-OH.

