# Statistical Methods, Data Analysis and Interpretation

Summary statistics will be used to describe demographic and clinical variables. A sample size of 40 will achieve a power of 80% and a level of significance of 5%, for detecting a mean of 8 mmHg in ΔSBP-3' between the ON and OFF states with a within subject standard deviation of 20 mmHg based on published data on the effect of levodopa on supine and standing blood pressure in people with PD. The main statistical analysis will be conducted using mixed-effects regression models (linear mixed models), which will allow for the correlation of repeated measures within subjects. The response variable in our models will be ΔSBP-3', and the primary predictors will be the ON vs. OFF levodopa state and the period (visit 2 versus visit 3). A random intercept will be included for each subject to account for the within-subject correlation. For analyses of secondary outcomes, we will fit a mixed effect model and adjust the p value for multiple comparisons using the Hochberg multiple comparison procedure. Changes in blood pressure and heart rate with active standing and indices of baroreflex cardiovagal and sympathetic noradrenergic function OFF levodopa will be compared between PD+OH and PD-OH with Student t tests.

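### Hochberg-adjusted difference tests on baroreflex indices expected not to change, with no margin or interval rule, move results towards the hoped-for reading of no alteration

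*Combined protocol and SAP*

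**What the plan says.** Under Statistical Methods, Data Analysis and Interpretation, the rule for secondary outcomes is: "we will fit a mixed effect model and adjust the p value for multiple comparisons using the Hochberg multiple comparison procedure". The family of tests is not listed.

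Under Objectives, Aim 1 states: "Secondary endpoints will include validated indices of baroreflex cardiovagal and baroreflex sympathetic noradrenergic functions". Aim 2 calls the same kind of indices its primary endpoint and gives the hypothesis: "We hypothesize that levodopa will not alter baroreflex cardiovagal and sympathetic noradrenergic functions in either PD+OH or PD-OH".

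The description of the Valsalva maneuver under Procedures names seven indices. Two are cardiovagal: the Valsalva ratio and BRS-V. Five are noradrenergic: the blood pressure difference at the end of Phase II, PRT, adrenergic baroreflex sensitivity, BRA-II and BRA-IV.

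No index has an equivalence margin, a confidence-interval criterion, an effect size or a power statement.

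**The concern.** Hochberg guards against declaring that an index changed when it did not. For these indices the sponsor expects no change, so the error that matters is missing a change that is real. A Hochberg-adjusted p-value is never smaller than the raw one. Where the only evidence on offer is a difference test, the adjustment can therefore move a result in one direction only, towards non-significance, and further as more indices join the family.

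The background section notes that clinicians may hold back levodopa in patients with orthostatic hypotension. A falsely reassuring statement that baroreflex function is unaffected would bear directly on that question.

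**Working it through.** **Step 1. Fix the SD scale by reproducing the plan's own sample size.** The plan sizes the trial "for detecting a mean of 8 mmHg in ΔSBP-3' between the ON and OFF states" "with a within subject standard deviation of 20 mmHg", at 80% power and a 5% level, and obtains N = 40. For a paired comparison, n = ((z_α + z_power) × SD / δ)².

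- One-sided 5%, 20 mmHg as the SD of the ON-OFF difference: ((1.645 + 0.842) × 20/8)² = 38.6, so 39. Noncentral-t power at 40 is 0.80. This reproduces N = 40.
- Two-sided 5%, same SD: 49.1, so 50. Power at 40 is 0.69 (noncentral t) to 0.72 (normal). This does not reproduce it.
- With 20 mmHg as the SD of a single measurement, the SD of the difference is 20√2 = 28.3 and n is 78 (one-sided) or 99 (two-sided). Neither reproduces it.

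The SD of the paired difference is therefore the scale that matches the plan, and it is used below. On that scale the plan's own primary effect is 8/20 = 0.4 SD.

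**Step 2. Inputs for the indices.** From the documents: N = 40, each participant tested ON and OFF, a period term in the model, and seven named indices. Assumed, because the documents are silent: a two-sided 5% level, a Hochberg family of exactly those seven, the size of the true shift, how many indices shift, and (for within-group figures) 20 participants per group.

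**Step 3. One index shifted, the other six unaffected.** The miss rate is P(|T| ≤ t_crit), with T noncentral t, df = N − 2 and noncentrality d√N. Hochberg finds the largest k for which the k-th smallest of m p-values is at most 0.05/(m − k + 1), and rejects those k hypotheses. With a single shifted index the operative threshold is close to 0.05/7 = 0.0071.

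For d = 0.5 and N = 40, the noncentrality is 0.5 × √40 = 3.16. The critical value is 2.024 at 0.05 and 2.844 at 0.05/7. The miss rates are 13.1% and 37.4%. Simulating the full Hochberg step-up gives 37%, at between-index correlations of 0 and 0.5.

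**Step 4. Vary the assumptions.**

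| Setting (two-sided 5%) | Miss rate per shifted index, unadjusted | With Hochberg | Ratio |
|---|---|---|---|
| N = 40, 0.5 SD, 1 of 7 shifted | 13% | 37% | about 2.8 |
| N = 40, 0.4 SD, 1 of 7 shifted | 31% | 61% | about 2.0 |
| N = 40, 0.6 SD, 1 of 7 shifted | 4% | 18% | about 4.3 |
| N = 40, 0.5 SD, all 7 shifted | 13% | 20-23% | 1.5-1.7 |
| N = 40, 0.5 SD, 1 of 12 shifted | 13% | 45% | about 3.4 |
| N = 20 (one group), 0.5 SD, 1 of 7 shifted | 44% | 75% | about 1.7 |
| N = 40, 0.5 of the single-measurement SD, 1 of 7 shifted | 41% | 71% | about 1.7 |

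The direction is the same in every row. The size is not.

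**Step 5. What happens once a margin exists.** Suppose each index is instead tested for equivalence against a margin of 0.5 SD (for illustration only), with seven independent indices and N = 40. One index lies exactly at the margin and the other six are unaffected. The false claim that this index is unaltered occurs in about 5% of trials unadjusted and about 3% with Hochberg. Raising an equivalence p-value makes the no-change claim harder. For the joint claim that all seven are unaltered, Hochberg makes no difference: it rejects all seven exactly when the largest p-value is at most 0.05, which is the unadjusted all-must-pass rule.

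**The case against.** **Hochberg may not reach the hypothesis at issue.** The no-change hypothesis for the indices appears only under Aim 2, where the indices are called primary, and Hochberg is stated for secondary outcomes. Aim 1's own hypothesis concerns the blood pressure drop. This stands in part: coverage of the Aim 2 tests is unclear, and the statistical section describes no within-group ON-OFF tests, so the 20-per-group figure is hypothetical. But the Aim 1 ON-OFF comparisons of the same indices are expressly secondary and fall under the rule, and they are the data that Aim 2 uses.

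**The real defect is the missing margin.** Largely right. The bias exists only while a non-significant difference test is taken as support for no change. A reader might infer that the same flaw would remain if a margin were added and Hochberg kept. Step 5 shows otherwise: Hochberg would then be unnecessary, and conservative for single-index claims.

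**The misreading is predicted, not planned.** Also right. Nowhere do the documents say that an adjusted p-value above 0.05 will be reported as showing an unaltered index. But they offer no other basis for judging the hypothesis, so the plan should rule that reading out.

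**Hochberg is conventional for secondary endpoints.** True for claims of change, and it should stay there.

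**Conclusion.** The concern holds in a limited form. As written, the plan pairs a no-change hypothesis with difference tests whose p-values are adjusted upward, and gives no margin or interval rule. In that setting the adjustment can only favour the hoped-for reading.

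A reader might take from the 13% to 37% figure that the plan nearly triples the chance of missing an effect. The documents do not support that as a general statement. It needs a 0.5 SD shift, a two-sided 5% level, a family of exactly seven, one shifted index and all 40 participants, and several of these are not in the plan. At the plan's own standardised effect of 0.4 SD the rate roughly doubles, from 31% to 61%, and the unadjusted test is itself not very sensitive. All seven indices come from the same Valsalva recordings, so a joint shift is plausible, and the rise is then only to about 20-23%.

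The primary endpoint analysis is not affected. This is a worthwhile, inexpensive correction to the secondary analyses and to Aim 2.

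**What to change.** In the statistical section:

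1. Restrict Hochberg to claims that levodopa changes a secondary index, list the family, and say whether it covers the Aim 2 tests of the same indices.
2. For the no-change hypotheses, report the unadjusted ON-minus-OFF estimate and confidence interval for each index, overall and within PD+OH and PD-OH.
3. State that a non-significant p-value, adjusted or not, will not be reported as evidence that an index is unaltered. A claim that no index is altered should require each index's unadjusted interval, at a stated confidence level, to lie within a pre-specified margin. No multiplicity adjustment is needed because every index must pass.

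Removing Hochberg alone would not be enough: an unadjusted interval that contains zero does not show absence of an effect.

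Cost: a few sentences, the work of choosing and justifying a margin per index before unblinding or analysis, and one column of intervals. No new data or participants are needed. No effect becomes harder to claim, and some unadjusted intervals will exclude zero by chance: for seven independent unaffected indices with 95% intervals, the chance of at least one is 1 − 0.95⁷ = 0.30. Keeping Hochberg for claims of change deals with that.

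### Aim 2 asks whether levodopa acts differently in PD+OH and PD-OH, but no written analysis estimates that difference for the baroreflex indices

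*Combined protocol and SAP*

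**What the plan says.** **Objectives, Aim 2.** The aim is: "Determine if levodopa has a different effect on cardiovascular autonomic function in participants with PD+OH compared to participants with PD-OH". Its endpoint is given as "The primary endpoint for AIM#2 will be indices of baroreflex cardiovagal and noradrenergic function", and its data source as "The data from autonomic testing performed for AIM#1 will be used to assess AIM#2". The hypothesis is that "levodopa will not alter baroreflex cardiovagal and sympathetic noradrenergic functions in either PD+OH or PD-OH"; no margin is given.

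**Objectives, Aim 1.** The same family of measures also appears here: "Secondary endpoints will include validated indices of baroreflex cardiovagal and baroreflex sympathetic noradrenergic functions".

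**Statistical Methods, Data Analysis and Interpretation.** Three statements bear on the point:
- For the change in systolic pressure at 3 minutes of tilt (ΔSBP-3'), "the primary predictors will be the ON vs. OFF levodopa state and the period (visit 2 versus visit 3" are named, with a random intercept per subject.
- "For analyses of secondary outcomes, we will fit a mixed effect model and adjust the p value for multiple comparisons", by the Hochberg procedure. No model terms are listed.
- The one sentence that names both groups covers active-standing changes and then the indices: "indices of baroreflex cardiovagal and sympathetic noradrenergic function OFF levodopa will be compared between PD+OH and PD-OH with Student t tests".

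**Sample Size.** A total of 40 is given, with no split between PD+OH and PD-OH.

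**The concern.** Aim 2 concerns a difference between two differences: the ON-OFF change in PD+OH minus the ON-OFF change in PD-OH. OH group is not named as a term in any model in the statistical section. The sole between-group test of the indices is confined to the OFF state. The ON-OFF effect within each group, which the Aim 2 hypothesis refers to, is not specified either.

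Followed as written, the plan produces no estimate of the quantity that one of its two aims is about. The model terms, the list of indices tested and the multiplicity treatment for Aim 2 could all be settled after the data are seen. There is also a risk of misreading: an OFF-state group difference could be reported under Aim 2 as though it bore on levodopa.

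**Working it through.** **1. The plan's own figure.** The only sample-size statement is for Aim 1: N = 40, 80% power, 5% significance, 8 mmHg, SD 20 mmHg. Taking 20 mmHg as the SD of the paired difference and a one-sided test, n = (20 × (1.645 + 0.842) / 8)² = 38.6, so 39. With the noncentral t, 40 participants give 80.0% power. A two-sided test would need 50 (normal) or 52 (t). So 40 reproduces on the one-sided paired reading, although the documents state neither sidedness nor that reading of the SD. The plan gives no figure for Aim 2.

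**2. What each analysis estimates.** Write the four cell means of an index, leaving period aside:

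| | OFF | ON |
|---|---|---|
| PD-OH | a | a + s |
| PD+OH | a + g | a + g + s + d |

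- Aim 2 quantity: [(a + g + s + d) − (a + g)] − [(a + s) − a] = d.
- OFF-state t test: (a + g) − a = g.
- Model with state and period only: one ON-OFF effect averaged over all participants.

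The OFF-state test contains no d, and the state-and-period model does not separate d from s.

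**3. Simulation check.** Settings: 5,000 runs, 20 per group, within- and between-subject SD 1, two-sided 5%.

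| True situation | OFF-state t test rejects | Test of ON-OFF difference between groups rejects |
|---|---|---|
| g = 1.5, d = 0 | 90% | 5% |
| g = 0, d = 1.5 | 5% | 91% |

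Used as an answer to Aim 2, the OFF-state test could mislead in either direction.

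**4. Precision of the missing contrast.** The documents give no SD for any index, so the unit is the SD of that index's ON-OFF difference. Assumptions: that SD is equal in both groups, testing order is balanced within group, the test is two-sided 5%, and all 40 have both tests. The splits are assumed.

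SE = √(1/n₁ + 1/n₂); half-width = 2.024 × SE (t, df 38); difference detectable with 80% power ≈ (2.024 + 0.851) × SE, which agrees with the noncentral t.

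| Split | SE | 95% CI half-width | 80% detectable, unadjusted |
|---|---|---|---|
| 20/20 | 0.316 | 0.64 | 0.91 |
| 15/25 | 0.327 | 0.66 | 0.94 |
| 10/30 | 0.365 | 0.74 | 1.05 |

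Counting period in the model (df 37) changes the 20/20 row only to 0.641 and 0.910. Within one group of 20, the ON-OFF half-width is 2.093 / √20 = 0.47.

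**The case against.** The best defence is that the mixed model for secondary outcomes covers Aim 2. The indices are secondary endpoints under Aim 1, the plan commits to a mixed model for such outcomes, and calling state and period the primary predictors leaves room for others. This stands in part: an interaction is permitted. But a sentence that lists no terms defines no contrast, and under Aim 2 the indices are the primary endpoint.

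A second defence is that the OFF-state t tests were never meant to answer Aim 2. The sentence also covers active-standing changes, and it reads naturally as a description of the groups without the drug. That is fair. A reader might infer that the plan designates the wrong test for Aim 2, or that it rules the interaction out. The documents support neither reading. The defect is that the right analysis is not written down.

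A third defence is that the precision figures are the same whether or not the interaction is prespecified, because they follow from 40 participants. That is correct. They describe what the fix can deliver and do not measure harm from the omission. The plan makes no Aim 2 power claim for them to contradict.

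**Conclusion.** The point holds and should be fixed before analysis. One of the two aims has no specified estimate, and the only stated group comparison of its endpoint addresses a different quantity. The Aim 1 primary analysis is not affected.

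This conclusion rests on the text and needs none of the numerical assumptions. The interaction half-width of about 0.64 SD (up to 0.74 at 10/30) does depend on them, and it is a limit of the remedy.

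Three stronger readings go beyond the documents:
- *That the Aim 2 terms will be chosen after the data are seen.* The documents show only that they could be.
- *That multiplicity raises the detectable difference by a known amount.* The Valsalva maneuver section lists seven indices, and the strictest Hochberg step for seven tests would need 1.17 SD at 20/20. But nothing commits the plan to testing all seven or only those, that step is the worst case of a step-up procedure, and the plan applies Hochberg to secondary outcomes while calling the indices primary for Aim 2. Whether it applies to Aim 2 is open.
- *That finding no significant change would confirm the Aim 2 hypothesis.* With no margin stated and intervals this wide, it would not, for the interaction or within either group.

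**What to change.** Add to the statistical section, before analysis:

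1. For each baroreflex index tested, a mixed model with levodopa state, period, OH group, group-by-state and a random subject intercept.
2. The group-by-state estimate with its 95% CI as the Aim 2 analysis.
3. The ON-OFF effect with its 95% CI within PD+OH and within PD-OH.
4. A label on the OFF-state t tests saying that they describe the groups and are not the Aim 2 test.
5. A list of the indices tested for Aim 2, and a statement of whether Hochberg applies to them and in which family. A separate Aim 2 family is one option. It would control error within each aim but not across both.
6. A statement that a non-significant interaction, or a non-significant ON-OFF effect within a group, is not evidence of no effect.

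The cost is two model terms per index and a few sentences. The plan already schedules ON and OFF testing in both groups, so no participants or visits are added. The drawback is imprecision: with 40 participants, only large differences in levodopa effect could be detected, and the report should say so.

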## **Background and Introduction**

Parkinson's disease (PD) is characterized by the gradual onset of motor symptoms such as bradykinesia, rigidity, tremor, gait difficulties and postural instability, as well as non-motor symptoms such as cognitive impairment and autonomic dysfunction among others [1]. Neurogenic orthostatic hypotension (nOH) is the main clinical manifestation of cardiovascular autonomic dysfunction [2]. The arterial baroreflex allows for beat-to- beat regulation of the blood pressure and heart rate via differential modulation of its cardiovagal (parasympathetic) and noradrenergic (sympathetic) efferent limbs [3]. Several mechanisms may contribute to nOH in PD including baroreflex-cardiovagal and baroreflex-sympathetic noradrenergic failure [2]. The prevalence of nOH in PD increases with age and disease duration; however, several studies have documented that nOH may appear early in the course of PD and reported prevalence of nOH in PD ranges from 30% to 65% [4, 5]. The presence of nOH in PD is associated with poor outcomes related to cardiovascular events, increased morbidity and mortality, more rapid disease progression, cognitive impairment, and falls [6].

Levodopa is a precursor of dopamine and is the treatment of choice to treat the motor symptoms of PD; however, the effect of levodopa on cardiovascular autonomic function in PD is poorly understood. Orthostatic hypotension has been documented as a potential side effect of levodopa in different studies [7, 8]. As a result, clinicians may be reluctant to prescribe levodopa in patients with PD with nOH (PD+OH), which leads to suboptimal management of motor symptoms. On the other hand, several studies failed to show any clear relationship between levodopa and orthostatic hypotension in patients with PD [9-12]. Important limitations of prior studies include the lack of detailed investigation of baroreflex cardiovagal and sympathetic noradrenergic functions and the fact that the same patients were not tested on and off levodopa.

We propose to investigate the effects of levodopa on cardiovascular autonomic function in patients with PD+OH and PD without nOH (PD-OH) by performing standardized autonomic testing in the same patients on and off levodopa.

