#### **Inclusion Criteria:**

## All participants:

- Age 18 or older
- Diagnosis of PD based on consensus criteria (Movement Disorder Society Criteria for Parkinson's disease) [13].

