#### For PD+OH group:

- Orthostatic hypotension defined by sustained drop in systolic blood pressure > 20 mmHg and/or a drop in diastolic blood pressure > 10 mmHg within 3 minutes from supine to standing during active standing or tilt [14].
- Autonomic testing and a ratio orthostatic heart rate change / systolic blood pressure change < 0.5 bpm/mmHg will confirm a neurogenic etiology [15].

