#### **Procedures:**

**Screening:** When the PI (or approved study personnel) makes contact with potential participant, basic information will be obtained to determine eligibility, including: medical history, PD diagnosis date and symptoms, current medications, among others.

Consent Process: Informed consent will be completed. Participants will complete the informed consent form on paper, or via REDCap. Participants will receive a paper copy per their request. Prior to signing the consent form, study personnel will thoroughly explain all study procedures and provide participants with ample time to ask any questions. The study team will continue to provide participants with opportunities to ask questions to ensure ongoing informed consent throughout the progress of the study.

Clinical assessment: The primary investigator will perform a medical history and physical examination before the testing procedures (baseline visit). The baseline visit will be performed on levodopa. The scales and assessments will include the Composite Autonomic Symptoms Score 31 (COMPASS 31), the Movement Disorder Society-Sponsored Revision of the Unified Parkinson's Disease Rating Scale (MDS-UPDRS) part I, II, III, and Hoehn and Yahr stage. The clinical assessment and scales are part of the standard of care in PD. Orthostatic vital signs (standing and supine measures of heart rate and blood pressure) will be performed during the baseline visit with active standing and the day of off-levodopa autonomic testing.

**Autonomic testing:** All participants will undergo autonomic testing on two separate days. The first autonomic testing will occur within 4 weeks of the baseline visit. The two autonomic tests will occur within a 2-week timeframe. To avoid any confounding of treatment effects and period effects, the order of testing (on versus off levodopa) will be randomized so testing on the first day will be on-levodopa for half of the participants and off-levodopa for the other participants. The procedures performed in this study are part of standardized clinical autonomic function testing. Autonomic testing will be performed by a research assistant with expertise in autonomic testing.

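### The covariate-free t tests between PD+OH and PD-OH describe the groups but cannot show that a baroreflex difference goes beyond age or disease duration

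*Combined protocol and SAP*

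**What the plan says.** Statistical Methods, Data Analysis and Interpretation states that "indices of baroreflex cardiovagal and sympathetic noradrenergic function OFF levodopa will be compared between PD+OH and PD-OH with Student t tests". No covariate is attached to these tests. The same section says "Summary statistics will be used to describe demographic and clinical variables", and gives those variables no other role. The primary mixed model names levodopa state and period as its primary predictors. The model for secondary outcomes names no covariates, and the group t tests are specified apart from it.

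The groups are formed by an observed characteristic. The inclusion criteria for the PD+OH group begin "Orthostatic hypotension defined by sustained drop in systolic blood pressure". What is randomised is something else: under Procedures, "the order of testing (on versus off levodopa) will be randomized". The age criterion for all participants is "Age 18 or older", with no upper limit. No matching, stratification or sensitivity analysis for age or disease duration appears anywhere.

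Background and Introduction says "The prevalence of nOH in PD increases with age and disease duration", and in the same sentence that "several studies have documented that nOH may appear early in the course of PD". Screening already collects "medical history, PD diagnosis date and symptoms, current medications, among others".

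**The concern.** The plan's own background gives a reason to expect that PD+OH participants may be older, or have had PD for longer, than PD-OH participants. If a baroreflex index also changes with age or duration, the two-sample t test combines that effect with whatever goes with OH and cannot separate the two. A reader of the results could then credit OH with a difference that partly reflects age or disease stage. These t tests are also the only PD+OH versus PD-OH comparison that the statistical section spells out, and they use the indices that Objectives names as the primary endpoint of AIM #2.

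**Working it through.** The plan gives no figure for this comparison, so there is none to reproduce. Its sample-size statement concerns the ON versus OFF change in systolic pressure and says nothing about the group contrast.

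**Inputs**
- From the documents: 40 participants in total (Sample Size); two-sample t test, no covariates (Statistical Methods).
- Assumed, because the documents are silent: 20 per group; two-sided 5% level; a standardised gap in age or duration of d = 0.5 to 0.8; a within-group correlation of the index with that variable of r = 0.3 to 0.5; linear effect.

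**Step 1: shift in the unadjusted difference.** In SD units of the index, shift = r × d.

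**Step 2: what the t test would do with that shift alone.** With no OH difference at equal age and duration, the noncentrality is shift / √(1/20 + 1/20) = shift / 0.316, on 38 degrees of freedom.

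| d | r | Shift (SD) | Noncentrality | Rejection at 5% |
|---|---|---|---|---|
| 0.5 | 0.3 | 0.15 | 0.47 | 7.5% |
| 0.8 | 0.3 | 0.24 | 0.76 | 11.5% |
| 0.5 | 0.5 | 0.25 | 0.79 | 12.0% |
| 0.8 | 0.5 | 0.40 | 1.26 | 23.4% |

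With no gap (d = 0) the rate is 5.0%. With a 12/28 split the shifts are unchanged and the rates for the first and last rows are 7.1% and 20.4%. For scale, 20 per group gives 80% power for a difference of about 0.91 SD, so a shift of 0.15 to 0.40 SD is 16% to 44% of that (0.15/0.91 and 0.40/0.91).

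**Step 3: does adjustment remove the shift?** In a simulation with one covariate and a linear effect (20,000 data sets per setting, 20 per group, d = 0.5 to 1.0, r = 0.3 to 0.7, no OH difference), the adjusted model rejected in 4.5% to 5.1% of data sets, and its mean bias was at most 0.004 SD in size.

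**Step 4: what two covariates do to precision.** Take age and duration as uncorrelated within groups, each with gap d and correlation r. The standard error of the adjusted difference relative to the unadjusted one is

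√[(1 + 10·D²/38) × (1 − R²) × 38/36], with D² = 2d², R² = 2r², and 10 = 20 × 20/40.

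- Best case, d = 0.5 and r = 0.5: √(1.132 × 0.50 × 1.056) = 0.77, a change of −23%.
- Worst case in the assumed range, d = 0.8 and r = 0.3: √(1.337 × 0.82 × 1.056) = 1.08, or +8%.
- Neither covariate predicts the index, d = 0.8 and r = 0: √(1.337 × 1.056) = 1.19, or +19%.

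If the two covariates are positively correlated, D² and R² are each divided by 1 + that correlation. At 0.5 the three results become −13%, +7% and +14%.

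**The case against.** The best reply is that these t tests describe the groups and serve no stated aim. AIM #1 compares ON with OFF within each participant. AIM #2 asks whether levodopa acts differently in the two groups, which is a comparison of ON-OFF changes. Neither hypothesis concerns OFF-state differences, and nothing in the plan claims independence from age. The Background also lists baroreflex failure among the mechanisms that may contribute to nOH, so age and duration could act through the very quantity being measured. Adjusting for them then answers a different question, and preferring that answer is a choice of estimand. Finally, no section links the indices themselves to age or duration, and the summary statistics might reveal any imbalance.

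Most of this stands. The unadjusted contrast is legitimate as description and should stay. The rejection rates in the working assume no OH difference at equal age and duration; given the Background, some difference is to be expected, so they are not realistic error rates for this trial.

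What does not follow is that nothing need be added. The plan specifies significance tests without labelling them descriptive or limiting how they are to be interpreted. Tabulating age and duration by group would show an imbalance, but not how much of an index difference goes with it.

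**Conclusion.** The point holds in a limited form. The planned t tests can show that PD+OH and PD-OH differ in OFF-levodopa baroreflex indices. They cannot show that the difference goes beyond age or duration. The possible shift of 0.15 to 0.40 SD is only an illustration: it rests on an assumed 20/20 split, gap and correlation, none of which the documents supply.

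A reader might infer more, but the documents do not support it:
- **That the t tests are wrong or should be dropped.** They are valid as description.
- **That the false-positive rate is 7.5% to 23%.** That needs both the assumed inputs and no OH difference at equal age and duration, which sits badly with the protocol's account of nOH.
- **That PD+OH participants will be older with longer disease.** The Background makes this plausible, but it also says nOH may appear early.
- **That the main result is biased.** The ON/OFF primary analysis uses each participant as his or her own control and is not affected.

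This is a cheap improvement to a secondary comparison, not the repair of an error in the primary analysis.

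**What to change.** In Statistical Methods, Data Analysis and Interpretation, keep the unadjusted group difference and label it descriptive. Then add that each OFF-levodopa baroreflex index will also be analysed in a linear model on OH group, age and years since PD diagnosis. Report the adjusted difference with its 95% CI beside the unadjusted one, and attribute a difference to OH beyond age and duration only on the adjusted estimate. Tabulating age and years since diagnosis by group would let readers judge the imbalance.

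The cost is a sentence or two of text and two degrees of freedom per model. No new data are needed, since age is an eligibility item and the diagnosis date is collected at screening. With 20 per group the standard error would change by about −23% to +8% under the assumed gaps and correlations of 0.3 to 0.5, and by up to about +19% if neither covariate predicts the index. With 40 participants the model should stay at these two covariates, named in advance.
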